8. STATISTICS

8.1. Sample Size Determination

This study will enroll approximately 340 subjects with a 1:1 randomization ratio to pamrevlumab or placebo, respectively.

A sample size of 340 subjects will have at least 90% power, based on a two-sided alpha level of 0.05 for a two-sample t-test, to detect a treatment difference of 120 mL in the primary efficacy endpoint, change from baseline in FVC (L), assuming a common standard deviation of 300 mL. This sample size allows for a dropout rate of approximately 20%.

The rationale for these sample size assumptions are as follows. In the phase 2 study FGCL-3019-067, a treatment difference of 178 mL was observed in change from baseline in FVC to Week 48. For this study, a conservative treatment difference of 120 mL is assumed. The standard deviation is estimated based on published results from other IPF studies.

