5.3.4. General Instructions of TLF

Follow the same guidelines as described in SAP for the double-blind period.

Summary tables will be presented for each previous actual treatment group in the double-blind period and all subjects pooled in the OLE period.

Efficacy and safety data will be summarized descriptively for subjects who entered OLE. No formal statistical inference will be performed.

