APPENDIX 2. ANALYSIS OF ASSOCIATION BETWEEN QLF AND OS

Cox proportional hazard (PH) analyses on the association between QLF and overall survival (OS) will be performed for the ITT population including both double-blind and OLE periods. The hazard ratio and its corresponding 95% CI between QLF Test Group vs QLF Reference Group. A stratified log-rank test stratified by randomization stratification factor will be used for treatment comparison.

No imputation will be performed on missing data. On-treatment analysis will be optional.

- QLF as a predictor:
- 1. To investigate whether baseline QLF is a significant predictor of mortality, a Cox PH model will include electronic data capture (EDC) GAP stage (I/II/III), and prior IPF treatment (Yes/No) as covariates, baseline QLF% (cutoff such as 15%, 20%, or 25%) as the predictor variable.
- 2. Similar analysis on baseline QLF volume (ml) will be performed as in 1), using baseline QLF volume (ml) (cutoff such as 300ml, 400ml, and 500ml) as the predictor variable.
- 3. In addition, Cox PH model including EDC GAP stage (I/II/III), and prior IPF treatment (Yes/No) as covariates, baseline QLF% or QLF volume (ml) (as a continuous variable) as the predictor variable, will be performed.
 - Change from baseline in QLF at Week 24 as a predictor
- 1. In addition, to investigate the association between change from baseline in QLF% (baseline to Week 24) and OS, the Cox PH model will include EDC GAP stage (I/II/III), prior IPF treatment (Yes/No), and baseline QLF% (as a continuous variable) as covariates, and category in change from baseline in QLF% (e.g., ≥2% vs <2%) as the predictor variable.
- 2. Similar analysis on QLF volume (ml) change from baseline will be performed as in 4) with baseline QLF% replaced with baseline QLF volume as a continuous covariate, and change from baseline in QLF volume (ml) as the predictor variable with a cutoff (e.g., ≥40 mL vs <40mL) will be performed.

STATISTICAL ANALYSIS PLAN

TITLE PAGE

A Phase 3, Randomized, Double-Blind, Placebo-

STUDY TITLE: Controlled Efficacy and Safety Study of Pamrevlumab in

Subjects with Idiopathic Pulmonary Fibrosis (IPF)

PROTOCOL NUMBER: FGCL-3019-095 (ZEPHYRUS 2)

FibroGen, Inc.

STUDY SPONSOR: [name]

[name]

STUDY DRUG: Pamrevlumab

INDICATION: Idiopathic Pulmonary Fibrosis (IPF)

PROTOCOL VERSION: Version 2.0

SAP VERSION Final V1.0 (Double-Blind Period)

RELEASE DATE: 12Jun2023

CONFIDENTIALITY STATEMENT

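### OLE SAP Appendix 2 relates Week 24 change in QLF to survival only through categories with illustrative cuts; a continuous model, as already planned for baseline QLF, would be a cheap gain in precision

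*SAP*

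**What the plan says.** All of this is in OLE SAP Appendix 2. The Cox analyses "will be performed for the ITT population including both double-blind and OLE periods".

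- **Baseline QLF.** Items 1 and 2 use cutoffs for QLF% and QLF volume. Item 3 then adds a model with "baseline QLF% or QLF volume (ml) (as a continuous variable) as the predictor variable, will be performed".
- **Week 24 change in QLF%.** The model uses "category in change from baseline in QLF% (e.g., ≥2% vs <2%) as the predictor variable". Baseline QLF% is a continuous covariate, but the change is not continuous.
- **Week 24 change in QLF volume.** The plan is "change from baseline in QLF volume (ml) as the predictor variable with a cutoff (e.g., ≥40 mL vs <40mL) will be performed", with baseline volume as a continuous covariate.
- **Missing data.** "No imputation will be performed on missing data".

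No continuous model for change is listed, and the double-blind SAP has no model of QLF against survival. Neither SAP nor the protocol gives a reason for 2% or 40 mL. For the OLE SAP as a whole, section 5.3.4 states: "No formal statistical inference will be performed".

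**The concern.** Change in QLF is a continuous measurement. With a 40 mL cut, a subject at +41 mL counts the same as one at +300 mL and differently from one at +39 mL. If risk rises steadily with change, that throws information away, and deaths will be few. The hazard ratio also depends on a cut that is given only as an example and could be settled after the data are seen. The appendix itself sees the value of a continuous term, since it adds one for baseline. At stake is the width of the confidence interval, and the chance of seeing a real association, in these two models.

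**Working it through.** **The plan's own power figure.** Protocol section 8.1 covers only the primary FVC endpoint: "This study will enroll approximately 340 subjects with a 1:1 randomization ratio", "based on a two-sided alpha level of 0.05 for a two-sample t-test", 120 mL difference, SD 300 mL, 90% power, about 20% dropout. Per arm: 2 × (1.960 + 1.282)² × (300/120)² = 2 × 10.51 × 6.25 ≈ 131.4, so 132, or 264 in total. Then 264/0.8 = 330, which agrees with 340. It reproduces, but it does not bear on Appendix 2, for which no power, event count or effect size is stated.

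**Inputs**

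| Input | Value | Source |
|---|---|---|
| Alpha | 0.05 two-sided | borrowed from protocol 8.1 |
| Subjects with a usable change | 272 = 340 × 0.8 | protocol 8.1 dropout, as a stand-in |
| Death rate | 9/103; × 340 = 29.7 by Week 48 | Phase 2 study, protocol 2.6.3 |
| Usable deaths D | 18 to 60 | assumed: deaths before the Week 24 scan drop out, OLE deaths add an unknown number |
| HR per SD of change | 1.3 to 1.5 | assumed |
| Share above the cut, p | 50%, 30%, 20% | assumed |
| Shape | normal predictor, linear log-hazard | assumed |

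**Closed form.** A cut with share p above it keeps e = φ(c)²/[p(1−p)] of the information, where c is the cut on the SD scale: 0.637 at the median, 0.576 at 30% and 0.490 at 20%. Power = Φ(√(D·e) × ln HR − 1.96), with e = 1 for the continuous term.

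- D = 45, HR 1.5. Continuous: 6.708 × 0.4055 − 1.96 = 0.760, power 78%. Median cut: 5.352 × 0.4055 − 1.96 = 0.210, power 58%. Loss: 19 points.
- D = 18, HR 1.3. Continuous: 4.243 × 0.2624 − 1.96 = −0.847, power 20%. Median cut: 3.385 × 0.2624 − 1.96 = −1.072, power 14%. Loss: 6 points.
- In terms of precision, a median cut inflates the standard error by 1/√0.637 = 1.25.

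**Simulation.** The closed form is a local approximation, so I fitted Cox models to simulated data: 272 subjects, follow-up to the D-th death, Wald test, 6,000 runs per case. Power in %:

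| HR per SD | Deaths | Continuous | Cut, 50% above | 30% above | 20% above | Loss, points |
|---|---|---|---|---|---|---|
| 1.3 | 18 | 21.0 | 12.8 | 15.0 | 15.4 | 6–8 |
| 1.3 | 30 | 30.0 | 19.1 | 21.9 | 21.4 | 8–11 |
| 1.3 | 60 | 52.2 | 35.8 | 36.5 | 35.0 | 16–17 |
| 1.5 | 18 | 40.3 | 23.9 | 29.0 | 29.2 | 11–16 |
| 1.5 | 30 | 60.2 | 39.2 | 42.9 | 41.6 | 17–21 |
| 1.5 | 45 | 77.5 | 55.8 | 57.3 | 56.3 | 20–22 |
| 1.5 | 60 | 88.0 | 68.5 | 70.4 | 66.2 | 18–22 |

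For upper-tail cuts the closed form overstates the loss. With 45 deaths, HR 1.5 and 20% above the cut, it gives 48% against 56% simulated. The simulated loss does not grow steadily as the cut moves off centre.

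**Other shape.** If the truth is a step at the median (HR 2.5 across it, 48 deaths), the correctly placed cut has 86% power and the continuous term 68%. With the same step but a cut at 30% or 20% above, the category has 51% or 34%.

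**The case against.** Four points on the other side carry weight.

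- **No fixed size.** A reader might infer that the categories cost about 20 points of power. The documents supply no deaths, effect or distribution, so that figure is a benchmark under chosen assumptions. Deaths before the Week 24 scan add no events, because missing data are not imputed. With few usable deaths neither model is well powered and the gap is small. Outside the range above it can nearly vanish: the closed form at 100 deaths and HR 1.8 loses under 1 point at all three cuts except 20% above, where it loses under 2.
- **Linearity is assumed.** A step at the cut reverses the ranking. This stands, but the category wins only if the cut sits close to the step, and the documents give no evidence of a step at 2% or 40 mL.
- **Low stakes.** Appendix 2 has no alpha allocation or decision rule. The treatment effect on QLF volume is already analysed as a continuous change by MMRM (double-blind SAP 6.7.2.2). Nothing supports reading the change models as a test of QLF as a marker of treatment response; the appendix says only that it looks at association with survival.
- **Parity has limits.** Item 3 is an addition to the cutoff models. A reader might infer that the continuous model should lead and the categories be demoted; the appendix's own precedent supports only adding it. For QLF%, the example wording also leaves the number of levels open, so a strict two-level reading is an interpretation.

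None of this explains why baseline gets a continuous model and change does not, or why the cuts are left open.

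**Conclusion.** The gap is real. Both Week 24 change models use categories with unjustified, illustrative cuts, and there is no counterpart to item 3. With a normal predictor, a linear log-hazard, HR 1.3 to 1.5 per SD and about 18 to 60 usable deaths, the loss is about 5 to 22 points of power. It is consistently near 20 only where the continuous model has about 75 to 90% power; it is 17 to 21 at about 60% and smaller below that. The documents cannot narrow this range, and a step at the cut would favour the category. An unconditional 20-point loss, or any effect on the trial's primary or secondary conclusions, is not supported. This is a cheap improvement to an exploratory analysis.

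**What to change.** In the Week 24 change part of OLE SAP Appendix 2:

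1. Add a Cox model with change in QLF% as a continuous covariate and, separately, one with change in QLF volume. Keep the same adjustment covariates and report the HR per fixed unit, for example per 1 percentage point and per 10 mL.
2. Add one linearity check for each, such as a quadratic or spline term.
3. Keep the categorical models, and fix their cuts before analysis.

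The cost is a few lines of SAP text and two more Cox models on data already held. The downside is the linearity assumption, which step 2 examines, and two more results to report in an analysis without multiplicity control.

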	pulmonary physiological parameters (P) - percentage predicted FVC [%], and
ССТ	percentage predicted DLCO [%]
GGT	Gamma-Glutamyltransferase
HAHA	Human Anti-Pamrevlumab Antibody
HRCT	High-Resolution Computed Tomography Informed Consent Form
ICH EO	
ICH E9	International Conference on Harmonization Statistical Principles for Clinical
ICC	Trials Immunogeniaity Analysis Set
IGS Confidential	Immunogenicity Analysis Set
Confidential	Page 9 of 56

Abbreviation	Explanation
IL-6	Interleukin-6
IL-8	Interleukin-8
INR	International Normalised Ratio
IP	
IPD	Investigational Product
IPF	Important Protocol Deviations
IRT	Idiopathic Pulmonary Fibrosis
ITT	Interactive Response System Intent-To-Treat
IV KL-6	Intravenous Veales van den Lyngen 6
	Krebs von den Lungen 6
L	Liter
LCQ LSMoon(s)	Leicester Cough Questionnaire
LSMean(s)	Least-Square Mean(s)
MAR	Missing At Random Markov Chain Monte Carlo
MCMC	
MedDRA	Medical Dictionary for Regulatory Activities
MI	Multiple Imputation
mL	milliliter Matrix Matalla Proteinaga 7
MMP7	Matrix MetalloProteinase-7
MMRM	Mixed Model for Repeated Measures
NMPA MNA B	China's National Medical Products Administration
MNAR	Missing Not at Random
OLE	Open Label Extension
OS	Overall Survival
PCS	Potentially Clinically Significant
PE	Physical Examination Pulmanary Experien Test
PFT PIIINP	Pulmonary Function Test
	Type III collagen Procellegen type I N terminal Properties
PINP PK	Procollagen type I N-terminal Propeptide Pharmacokinetic
PopPK PPS	Population Pharmacokinetic Per-Protocol Set
PROs	
PKOS PT	Patient Reported Outcomes Prefer Term
Q3W QLF	Every 3 Weeks Quantitative Lung Fibrosis
RBC	Red Blood Cell, or Erythrocyte
RCM	Random Coefficient Model
SAE	Serious Adverse Event
SAE SAF	Safety Analysis Set
SAP	Statistical Analysis Plan
SD	Standard Deviation
SE SE	Standard Error
SE	Standard Entit

Confidential Page 10 of 56

Abbreviation	Explanation
SGRQ	St. George's Respiratory Questionnaire
SOC	System Organ Class
TEAE	Treatment-Emergent Adverse Event
TESAE	Treatment-Emergent Serious Adverse Event
TGF-beta	Transforming Growth Factor beta
TLC	Total Lung Capacity Volume
TLF	Table, Listing, and Figure
TNF	Tumor Necrosis Factor
UCSD-SOBQ	University of California San Diego – Shortness of Breath Questionnaire
ULN	Upper Limit of Normal, value provided by the laboratory
VEGF	Vascular Endothelial Growth Factor
WHODD	World Health Organization Drug Dictionary
WOCBP	Women Of Childbearing Potential

Confidential Page 11 of 56

1. INTRODUCTION

This statistical analysis plan (SAP) is for the pre-specified reporting of study results for protocol FGCL-3019-095, amendment 2.0. Specifications of tables, data listings, and figures (TLF) are contained in a separate document. The statistical analyses and summary tabulations described in this SAP will provide the basis for the results section of the clinical study report (CSR). The SAP will be finalized prior to unblinding after the study Database Lock (DBL). Any major modification to this SAP after the signoff will be documented in an SAP amendment or CSR.

This SAP describes the planned statistical analyses for the double-blind period of the study. Statistical analyses for the main study cohort of subjects are planned for inclusion in the body of the CSR.

The open-label extension period (OLE) of the study will have a separate SAP. Additionally, a population pharmacokinetic (PopPK) analysis as well as an exposure-response analysis will be defined in a separate pharmacokinetic (PK) analysis plan.

Based on regional regulatory filing needs, region-specific subset analyses may be performed following the methodology outlined in this SAP. Refer to Appendix 7 if regulatory submission in China is pursued.

2. STUDY OBJECTIVE

The overall objective of this trial is to evaluate the efficacy and safety of 30 mg/kg intravenous (IV) infusions of pamrevlumab as compared to placebo in subjects with Idiopathic Pulmonary Fibrosis (IPF).

3. STUDY DESIGN

3.1. Overview

This is a Phase 3, randomized, double-blind, placebo-controlled multi-center trial to evaluate the efficacy and safety of pamrevlumab in subjects with IPF. Approximately 340 subjects will be enrolled in this trial.

3.2. Sample Size

A sample size of 340 subjects will have at least 90% power, based on a two-sided alpha level of 0.05 for a two-sample t-test, to detect a treatment difference of 120 mL in the primary efficacy endpoint, change from baseline in forced vital capacity (FVC, in Liter: L), assuming a common standard deviation of 300 mL (allowing about 20% dropout rate).

The rationale for these sample size assumptions is as follows. In the phase 2 study FGCL-3019-067, a treatment difference of 178 mL was observed in change from baseline in FVC to Week 48. For this study, a conservative treatment difference of 120 mL is assumed. The standard deviation is estimated based on published results from other IPF studies.

Confidential Page 12 of 56

3.3. Randomization and Treatment Assignment

Subjects will be randomized in a 1:1 ratio to one of the two study treatment arms as follows:

- Arm A: pamrevlumab, 30 mg/kg IV, Q3W (every 3 weeks)
- Arm B: matching placebo IV, Q3W

Randomization is stratified by GAP stage (I, II, III) derived from the GAP score obtained at screening (Refer to Appendix 6). Calculation of the GAP score for randomization is based on the Best-Test Review (BTR) assessment provided by the independent central spirometry vendor reader.

3.4. Study Periods

[figure not shown]
This study consists of the following study periods (Figure 1):

- Main (double-blind, placebo-controlled) study period:
 - Screening period: Up to 6 weeks
 - Treatment period: 48 weeks
- Optional, open label extension (OLE) period:

Access to pamrevlumab during the OLE period will be available until the last enrolled subject completes 48 weeks of treatment in the OLE period, or pamrevlumab is commercially available for the indication of IPF, or the Sponsor decides to end the OLE period, whichever occurs first.

- Follow-up period/final safety assessment:
 - 28 days after the last dose: scheduled visit
 - 60 days after the last dose: follow-up phone call, for a final safety assessment

Figure 1: Study Schema

The intent for this study is to evaluate the efficacy and safety profile of pamrevlumab as monotherapy in subjects with IPF who were previously treated with an approved therapy but

Confidential Page 13 of 56

who discontinued that therapy (possible reasons for discontinuation of approved therapy could include, but are not limited to, intolerance or disease progression), unless neither treatment is available in the host country.

After randomization and during the treatment period, co-administration of an approved IPF therapy (i.e., pirfenidone or nintedanib) is permitted if clinically indicated in the Investigator's opinion, provided that the Investigator assesses the potential risks/benefits of combining approved IPF therapies with blinded study treatment.

Subjects who complete the Week 48 visit of the main study (regardless of the number of study drug infusions received and or treatment group assigned in the double-blind period) will be eligible to participate in the optional OLE period of the study that offers continuing access to pamrevlumab regardless of randomization assignment in the main study.

Subjects who discontinue study treatment for any reason are encouraged to remain in the study and be followed for all study visits and assessments.

The following assessments will be assessed centrally by independent external vendors or study committees:

- Pulmonary function tests (PFTs)
- High-resolution computed tomography (HRCT)
- Acute IPF exacerbations and respiratory hospitalizations

In addition, an independent Data Monitoring Committee (DMC) will review safety data and other clinical data (with the authority to unblind such data) on a periodic basis to monitor overall subject safety.

4. STUDY ENDPOINTS

4.1. Primary Endpoint

• Change in Forced Vital Capacity (FVC) from baseline at Week 48

4.2. Secondary Endpoints

- Time to disease progression, defined as absolute Forced Vital Capacity percentage predicted (FVCpp) decline of ≥10% or death, whichever occurs first
- Time to the first occurrence of any component of clinical composite endpoint: acute IPF exacerbation, respiratory hospitalization, or death, whichever occurs first
- Change in Quantitative Lung Fibrosis (QLF) volume from baseline at Week 48
- Time to first acute IPF exacerbation during study
- Time to all-cause mortality during study
- Time to first respiratory hospitalization during study

Confidential Page 14 of 56

4.3. Exploratory Endpoints

- Time to composite of: respiratory hospitalization, absolute FVCpp decline ≥10%, or all-cause death, whichever occurs first
- Change in absolute FVCpp from baseline at Week 48
- Change in relative FVCpp from baseline at Week 48
- Change in St. George's Respiratory Questionnaire (SGRQ) score from baseline at Week 48
- Change in University of California San Diego Shortness of Breath Questionnaire (UCSD-SOBQ) score from baseline at Week 48
- Change in Leicester Cough Questionnaire (LCQ) from baseline at Week 48

4.4. Safety Assessments

- Treatment-emergent adverse events (TEAEs) and treatment-emergent serious adverse events (TESAEs)
- Clinical laboratory parameters
- Vital signs
- Immunogenicity (Human Anti-Human Antibody [HAHA] formation, also named ADA: anti-drug antibody)
- Hypersensitivity/anaphylactic reactions

4.5. Exploratory Biomarker Endpoints

Biomarkers to be analyzed may include but are not limited to:

- Connective Tissue Growth Factor (CTGF)
- markers of inflammation such as C-reactive protein (CRP), tumor necrosis factor (TNF), interleukin-6 (IL-6), interleukin-8 (IL-8), and chemokine (C-C motif) ligand 18 (CCL18)
- markers of fibrosis and collagen synthesis such as transforming growth factor beta (TGF-beta), procollagen type I N-terminal propeptide (PINP), and type III collagen (PIIINP)
- other markers of tissue remodeling and angiogenesis such as angiopoietins, vascular endothelial growth factor (VEGF), matrix metalloproteinase-7 (MMP7), and Krebs von den Lungen 6 (KL-6).

Confidential Page 15 of 56

5. GENERAL STATISTICAL CONSIDERATIONS

5.1. General Conventions

All data collected will be included in the data listings. All analyses will be performed using SAS® Version 9.3 or higher.

5.1.1. Analysis of Categorical Endpoints

Frequency distributions (number and percentage of subjects) will be presented for categorical variables.

5.1.2. Analysis of Continuous Endpoints

For continuous variables, descriptive statistics, including n, mean, standard deviation (SD), median, minimum, and maximum, will be presented.

Line graphs of group mean (and standard error: SE) and mean change from baseline (and SE) values will be plotted over visits as appropriate. Additional plots such as Least-square mean (SE) or boxplot will be provided as appropriate.

5.1.3. Analysis of Time-to-Event Endpoints

Kaplan-Meier curves for time-to-event endpoints will be plotted as appropriate. Comparisons of the respiratory hospitalization and acute IPF exacerbation endpoints will be based on the events identified by the Independent Adjudication Committee in accordance with the Adjudication Charter.

5.1.4. Analysis of Spirometry Data

All spirometry results are reviewed by the independent spirometry Over-Reader group for quality, during their Best Test Review (BTR). The Over-Reader does an overall quality rating of the spirometry data ("acceptable", "borderline acceptable" or "unacceptable") and determines which is the "Best" FVC (L) value and corresponding FVCpp for each test.

For each visit, only one FVC value and corresponding FVCpp that is identified by the Over-Reader as the "Best" FVC value, with an overall quality rating of "acceptable" or "borderline acceptable" will be used for analyses.

NOTE: A BTR is performed for each spirometry. In the situation where at a visit multiple spirometries were performed, the result considered for the analyses will be selected as follows:

Definition of "Best" post-BTR FVC value (and correlated FVCpp value): The "Best" value will be defined as that which meets the following criteria: (1) FVC value was selected after BTR by over-reader as the best test result; and (2) Result received an acceptable or borderline acceptable BTR rating.

• For the Day 1 assessment (Baseline), the "Best" post-BTR FVC value (and correlated FVCpp value) as defined above which also meets the following criteria will be used: (1) PFT was performed on or prior to Day 1; and (2) Result met eligibility criteria,

Confidential Page 16 of 56

that is, correlated FVCpp value was within the range of >45% and <95%. The qualifying Day 1 value will be used whenever a qualifying Day 1 value is available; otherwise, the qualifying value on the last visit prior to Day 1 will be used. In cases where there is more than one set of PFTs performed on the same day, the highest of the multiple qualifying values will be used.

• For all subsequent (post-Day 1) visits, the "Best" post-BTR FVC value (and correlated FVCpp value) as defined above which correlates with the study visit will be used for FVC and FVCpp analyses.

